**Randomized Clinical Trial (RCT) protocol**  
**5/30/2023**

**Principal Investigator (PI):**  
**[name], MS**

**NCT 04288115**

**Aim. Evaluate the feasibility of LT4 discontinuation among Veterans with SCH and determine the changes in quality-of-life measures, treatment burden, and adverse events.**

Design: Double-blind, placebo-controlled randomized clinical trial

Performance site: CAVHS

Participants: Fifty veterans with LT4-treated SCH will be randomized to either (1) continue current dose of LT4 [pre-study dose] or (2) placebo. Up to 150 veterans will need to sign consent and HIPAA authorization to reach 50 randomized participants due to the anticipated screen failure rate. The screen failure rate accounts for participants whose baseline lab results (TSH, FT4 and LDL) are out of study range. Participants will be identified from CDW/Strategic Management (Aim 1) and referrals from CAVHS providers (including Primary Care or Endocrine clinic providers).

Exclusion Criteria: (1) TSH > 10 mIU/L (at any point), (2) LT4 dose more than 75 mcg daily, (3) use of antithyroid medications, amiodarone, tyrosine kinase inhibitors or lithium, (4) history of thyroidectomy or radioactive iodine therapy, (5) LT4 suppressive therapy for thyroid cancer, goiter or inflammation, (6) pregnancy or plans for pregnancy in the next 6 months, (7) an unstable medical condition that would jeopardize safety or interfere with study participation, (8) hospitalization for major illness within the previous 4 weeks, (9) severe hypothyroidism-related symptoms, (10) strong family history of hypothyroidism, (11) severe dyslipidemia, (12) acute coronary artery syndrome, acute myocarditis, or pancarditis or stroke within the previous 12 months, (13) Grade IV New York Heart Association (NYHA) heart failure, (14) receiving services from hospice, (15) lack of decision-making capacity, (16) terminal medical condition for which life expectancy would be less than 6 months, (17) not willing to stop LT4, (18) self-reported non-adherence to LT4 therapy and (19) abnormal TSH at time of screening for participation (assessed during Baseline Visit). Pregnancy testing will be performed for females of child-bearing potential that sign consent to participate in the study. The results will be reviewed prior to randomization.

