Recruitment: We will send an **IRB-approved opt-out letter** to eligible veterans identified from CDW/Strategic Management or referral from CAVHS provider. The Principal Investigator (PI) has presented the study background, goals, and procedures to endocrinologists and primary care clinicians at CAVHS, answered questions, and got feedback from them (Development phase). A post-presentation poll of primary care physicians showed that 75% felt that LT4 discontinuation was acceptable in patients with SCH and 97% were comfortable with randomization of their eligible patients in the study. All endocrinologists felt that LT4 discontinuation was acceptable in patients with SCH and were comfortable with randomization of their eligible patients in the study. Clinicians were informed that Veterans under their care may be invited to participate and that those Veterans may want to discuss participation with their clinicians prior to enrolling. Before beginning to recruit, we will repeat the presentation to CAVHS clinicians who might prescribe LT4, including primary care, medicine, and endocrinology service clinicians, to refresh their memories and ensure that we reach clinicians new to CAVHS. In addition, an email with materials describing the study will be sent to clinicians who miss the presentation. Clinicians will be invited to contact the PI if they have questions or concerns about the study. The PI will utilize the Medicine and Primary Care quarterly conference to update clinicians. Study staff will send up to 100 IRB-approved opt-out letters weekly until all eligible veterans identified are sent the letter or 50 veterans are randomized (whichever occurs first). The pool of potential participants will be identified from CDW/Strategic Management and referrals from CAVHS providers. Women and minorities will be included in the study in proportion to their presence among CAVHS patients. We will submit and get approval for a **telephone script**. The designated study staff will call potential participants, with varying lengths of LT4 therapy, that do not opt-out (after at least two weeks from the mail date of the opt-out letter) and use the IRB-approved telephone script to guide the conversation.

Consenting: Written ICF and HIPAA will be obtained by the designated study staff prior to any study activities.

Intervention: (1) Continue current dose of LT4 [control or “sham discontinuation”] or (2) placebo [intervention or “real discontinuation”]

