Data Collected: (1) **Baseline Visit:** ICF, HIPAA, medical history, demographics, Vital signs (blood pressure and pulse, height and weight), study questionnaires (ThyPRO Hypothyroid symptoms and Tiredness scales, EQ-5D ThyPRO-39) and blood sample collection (TSH, FT4, lipids). (2) **Telephone Visit 1** (Month 1 +/- 3 days): Adverse event assessment and study medication compliance assessment. (3) **Clinic Follow-up 1** (6-8 weeks post randomization): Vital signs (blood pressure and pulse, weight), study questionnaires (ThyPRO Hypothyroid symptoms and Tiredness scales, EQ-5D), study medication compliance assessment, adverse event assessment and blood sample collection (TSH, FT4, TPO antibodies). (4) **Telephone Visit 2** (Month 3 +/- 3 days): Adverse event assessment and study medication compliance assessment. (5) **Telephone Visit 3** (Month 4 +/- 3 days): Adverse event assessment and study medication compliance assessment. (6) **Telephone Visit 4** (Month 5 +/- 3 days): Adverse event assessment and study medication compliance assessment. (7) **Clinic Follow-up 2** (Month 6 +/- 3 days): Vital signs (blood pressure and pulse, weight), study questionnaires (ThyPRO Hypothyroid symptoms and Tiredness scales, EQ-5D, ThyPRO-39, End of Study survey), study medication compliance assessment, assessment of integrity of blinding, disclosure of study medication assignment to participant, blood sample collection (TSH, FT4, blood lipids), duration of LT4 therapy and return to usual care plan. (8) **Unscheduled Visit:** an unscheduled visit(s) may be performed during the study. The unscheduled visit may be completed by telephone or in-person. Possible reasons for an unscheduled visit include safety assessment (such as lab collection for assessment of possible adverse event), repeat lab collection (test error or result confirmation), early termination (participant, Investigator, or joint decision) and/or study medication resupply.

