Planned Analysis: Initial data analysis will include descriptive statistics for all variables, including assessment of potential outliers and the extent of missing data. If the missing data rate is small, < 5%, and found to be at random, then complete case analyses will be performed; otherwise, multiple imputation strategies will be explored. Data will be presented as frequencies for categorical variables and means (standard deviations) for continuous variables. We will compare characteristics between groups using t-tests for quantitative variables and chi-square tests for categorical variables. For the primary outcome, intervention feasibility, we will calculate participants' willingness to enter the trial (percent of eligible Veterans approached who consented to participate), recruitment rate (number of patients randomized divided by the length of the recruitment period, i.e., from the date that recruitment opened to the date of the last randomization). These measures will shed light on the anticipated acceptability of LT4 discontinuation. Finally, we will calculate completion rate for each arm. Secondary outcomes include changes from baseline to 6 months in the ThyPRO Hypothyroid Symptoms and Tiredness scores, EQ-5D, ThyPRO-39 and blood lipids. We will also assess changes in weight, body mass index, blood pressure,

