*Compliance and Withdrawal:* We will provide an **IRB-approved pill diary** to all study participants. The study team will assess study medication compliance throughout the study. The pill diary may be reviewed at the follow-up clinic visits. Study medication compliance will be considered good if the participant reports taking study medication 80-100% of the time. **Participants may decide not to continue the study medication (LT4 or placebo) at any time. Additionally, the PI may decide not to continue the study medication for an individual (for example, following lab results). We will assist the participant to ensure that appropriate medication, if any, is started at the time of study medication discontinuation. If this occurs, the participant will be asked if they will continue the study (including follow-up visits, blood collection and study questionnaires) without continuing the study medication. If the participant agrees, they will be followed per protocol. If the participant does not agree, they will be classified as withdrawn from the study. We will document this occurrence, reason for discontinuation of study medication and participant decision to continue participation in the study (visits, blood collection and study questionnaires). Participants may agree to all or some of the study procedures.** We will instruct participants who discontinue the study

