medication to dispose of any unused study medication in the manner in which they usually dispose of expired medications or offer to have them return the unused study medication to CAVHS. Participants may withdraw from the study at any time. Withdrawal by the participant will be defined as any participant that informs the study team that they do not wish to continue the study medication, do not wish to allow any further collection of data, and do not wish to have any further contact with the study team. If they do so, they will be considered withdrawn voluntarily from the study. We will document the circumstance(s) and reason(s) for participant withdrawal. The PI may also withdraw participants from the study. This may occur in the event of inter-current illness, adverse events, protocol violations, non-compliance, or administrative reasons. We will assist the participant to ensure that appropriate medication is started at the time of withdrawal. We will instruct participants who withdraw (or are withdrawn) from the study to dispose of any unused study medication in the manner in which they usually dispose of expired medications or offer to have them return the unused study medication to CAVHS. Participants withdrawn from the study will not be replaced. To avoid breaking the blind, results of Visit 1 (Month 2) laboratory tests will not be published in CPRS but will be recorded in the Veterans Information Systems and Technology Architecture (VISTA), which is not used by clinicians for lab review. These lab results will be reviewed by Unblinded Personnel.

**Randomization Lab Criteria:** Baseline lab results (TSH, FT4 and lipid profile) will be reviewed prior to randomization by the Investigator or SC. To qualify for randomization, TSH and FT4 must be within normal reference range and LDL must be  $\leq 190$  mg/dL. Normal reference range for TSH: 0.54 – 5.6 mIU/mL. Normal reference range for FT4: 0.47 – 1.41 ng/dL.

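### Good compliance is defined by self-reported capsules alone and no listed follow-up contact asks about non-study LT4, so a placebo participant also taking home LT4 would be rated compliant (minor, cheap to improve)

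*Combined protocol and SAP*

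**What the plan says.** The Intervention paragraph compares continuing the pre-study LT4 dose with placebo, and the placebo arm is the discontinuation arm. The Aim is the feasibility of stopping LT4.

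Compliance and Withdrawal supplies a pill diary and sets the standard: "Study medication compliance will be considered good if the participant reports taking study medication 80-100% of the time". LT4 from any other source does not enter the definition.

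Data Collected itemizes six scheduled contacts after baseline. Each of the four telephone visits lists "Adverse event assessment and study medication compliance assessment" and nothing else. The two clinic visits also list the compliance assessment, with vital signs, questionnaires and blood tests. The only follow-up item that names LT4 is at Month 6: "duration of LT4 therapy and return to usual care plan". It is not explained. Recruitment speaks of calling people "with varying lengths of LT4 therapy", so the Month 6 item may simply mean treatment history.

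On laboratory values, Randomization Lab Criteria says: "To qualify for randomization, TSH and FT4 must be within normal reference range". Study Medication Discontinuation Criteria stops the capsules when TSH or FT4 crosses set limits. Planned Analysis promises that "Initial data analysis will include descriptive statistics for all variables", but nothing there ties TSH or FT4 to adherence.

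**The concern.** Adherence in the placebo arm has two parts: taking the capsules and taking no other LT4. The plan measures only the first. Everyone enrolled was already on LT4, and the documents describe no collection of home tablets and no hold on the usual prescription, so taking both is possible.

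Completion rate by arm is part of the primary feasibility outcome. Without a record of non-study LT4, the pilot cannot tell whether a placebo participant who completed had finished a course of capsules or had actually gone without LT4. The pilot is also meant to supply effect sizes for the full-scale trial. If stopping LT4 does worsen symptoms, co-use shrinks that estimate by an unknown amount. Co-use that is not asked about during follow-up cannot be reliably recovered afterwards.

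The point concerns people who take both. Those who openly stop the capsules and resume LT4 are already documented under Compliance and Withdrawal.

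**Working it through.** **1. Would the laboratory rules catch it?** Units are printed inconsistently between the two sections; I read TSH as mIU/L and FT4 as ng/dL throughout.

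| | Entry limits | Range with no stop |
|---|---|---|
| TSH | 0.54 to 5.6 | 0.34 to 10 |
| FT4 | 0.47 to 1.41 | 0.47 to 1.41 |

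The entry limits lie inside the no-stop range. A placebo participant who keeps taking the usual home dose stays on the regimen that met the entry limits, so probably triggers no rule. In the LT4 arm, co-use roughly doubles the dose. Because the exclusions include "LT4 dose more than 75 mcg daily", the maximum is 75 + 75 = 150 mcg. That could push TSH below 0.34 or FT4 above 1.41, but it would be at most an arm-level warning and would not identify placebo users.

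**2. What would co-use do to the ThyPRO tests?** Inputs from the plan are the margin of 14 points and one-sided alpha of 0.05 (Planned Analysis), and SD 20 and 23 per group (Sample size estimates). I use a two-sample t-test, without the ANCOVA covariates.

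- SE = 20 × √(2/23) = 5.898; df = 44; critical t = 1.680.
- Plan's own figure: with no true difference, the shift is 14/5.898 = 2.374 and power is 75.6%, against the stated 80%. A 14-point margin needs 26 per group for 80%. The sample size paragraph does not restate its margin. That gap is a separate matter and does not bear on this point.

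Let D be the true harm of stopping, c the share of placebo participants also taking LT4, and k the share of LT4 benefit they keep. The values of D, c and k are assumptions.

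- Expected difference = D(1 − ck).
- P(declare non-inferior) comes from the noncentral t with shift (14 − D(1 − ck))/5.898.

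Example: D = 14, c = 0.10, k = 1 gives 14 × 0.9 = 12.6 points, shift 1.4/5.898 = 0.237, and probability 7.9%.

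| True harm D | k | c = 0 | c = 0.10 | c = 0.20 |
|---|---|---|---|---|
| 0 | any | 75.6% | 75.6% | 75.6% |
| 7 | 1 | 31.7% | 36.0% | 40.4% |
| 7 | 0.5 | 31.7% | 33.8% | 36.0% |
| 14 | 1 | 5.0% | 7.9% | 12.0% |
| 14 | 0.5 | 5.0% | 6.3% | 7.9% |

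With one co-user in 23, D = 14 and k = 1, the probability is 6.1%. Only the D = 14 rows are false non-inferiority rates; at D = 7 non-inferiority is true. The expected difference with k = 1 falls from 7.0 to 6.3 and 5.6 points, or from 14 to 12.6 and 11.2. A simulation of 200,000 runs that adds the extra variance from mixing co-users with others gives 5.0%, 7.8% and 11.7% for D = 14, k = 1.

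**3. What would recording co-use change?** Nothing in the table. Analysis is by intention to treat, so a known co-user stays in the placebo arm and the test result is the same.

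**The case against.** The strongest reply is that recording co-use repairs no planned result. The compliance label feeds no stated analysis: Planned Analysis has no per-protocol set and no adherence-adjusted estimate. Consent and recruitment rates are untouched. All of this stands, and it limits the point to interpretation.

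Second, the content of the compliance assessment, the diary, the End of Study survey and the source forms is not shown. A reader might infer that nobody asks about home LT4. The documents support only that the visit list does not say so.

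Third, co-use has little motive. The exclusion "17) not willing to stop LT4" screens willingness at entry. Safety Considerations lets anyone return to their earlier medication at any time, and Compliance and Withdrawal lets those who stop capsules remain in follow-up. The consent discussion checks understanding of the medication schedule, a chart note tells routine clinicians about the study, and the PI may withdraw participants for non-compliance. These lower the likely rate. None of them records whether co-use happened.

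Fourth, TSH and FT4 are drawn from everyone at baseline, 6-8 weeks and Month 6, so change over time is available. By arm this is informative. For an individual it is weak: TSH need not rise in every placebo participant, so a normal value does not separate a co-user from someone who does well without LT4.

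**Conclusion.** The point holds as a minor, inexpensive improvement to a 50-person pilot. On the stated rule, a placebo participant taking both capsules and home LT4 is rated compliant. Completion is not defined in terms of LT4, so that person would presumably also count as completing, and the laboratory limits would probably not reveal it.

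The size is unknown. The 5.0% to 12.0% range assumes true harm exactly at the 14-point margin, co-use of 0 to 20% and full benefit kept; half benefit gives at most 7.9%, and no harm gives no effect.

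A reader might infer that the plan's non-inferiority tests run at 12% error, or that the added question would bring the rate back to 5%. The documents support neither: they give no co-use rate, and the intention-to-treat tests would be identical with or without the record. Nor does the gap invalidate the trial, since the ThyPRO comparisons are secondary. What is lost is the ability to say whether placebo-arm completion was real discontinuation and how far the effect estimate is diluted.

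**What to change.** - In Compliance and Withdrawal, define good compliance as 80-100% of study capsules and no non-study LT4 while on capsules.
- Add one question on non-study LT4 to the compliance assessment at each of the six existing follow-up contacts. If the forms already ask, say so in the protocol instead.
- State what the Month 6 duration item records.
- After unblinding, report non-study LT4 use by arm, separately from documented capsule stops and beside TSH and FT4 by arm.
- Optionally, add a VA refill query from randomization to Month 6. It shows neither ingestion nor use of tablets already at home.

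The cost is slightly longer contacts, one table and submission of the changed source forms to the IRB, which Data Management requires before use. No visits or blood draws are added. The answers still rest on self-report.

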and pulse. Analysis of covariance (ANCOVA) models will be employed to analyze these outcomes. Baseline measures and gender will be included in the models as covariates. A one-sided t-test will be used to determine whether the mean ThyPRO Hypothyroid Symptoms and Tiredness scores for the real discontinuation group differ from the mean ThyPRO Hypothyroid Symptoms and Tiredness scores of the sham discontinuation group by no more than 14 points. An  $\alpha$ -level of 0.05 will be used to determine the statistical significance of the non-inferiority test for each ThyPRO domain. Failure to reject the null hypothesis will suggest that the QoL measures in the real discontinuation group, on average, are more than 14 points worse than in the sham discontinuation group. This will be considered as evidence against our conjecture that discontinuation does not negatively affect the QoL of patients with SCH. In addition, analyses comparing groups with respect to adverse event rates will be performed using chi-square tests. Analyses will be based on the intention-to-treat principle. Statistical analyses will be done using SAS 9.4 (SAS Institute, Cary, NC).

*Additional details Analysis Plan:* We will add a Biostatistician to the project. They will be hired through an IPA to work on the project. The Biostatistician will be sent the data set by encrypted email and will use computer software on their laptop (non-VA) to complete the analysis. No name, date of birth or SSN will be included in the data set for analysis. Those data points will remain within the VA protected environment.

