**Study Medication Discontinuation Criteria:** The Unblinded Personnel will notify Blinded Study Personnel (SC) if a participant develops OH or hyperthyroidism. At which point, the SC will be unblinded. Results will be communicated to participants and treating physicians by Unblinded Study Personnel and/or SC. The participant will be followed per protocol (following discontinuation of study medication) unless they decide to withdraw from the study at the time of study medication discontinuation. Lab criteria for study medication discontinuation: (1) TSH  $> 10$  mIU/mL or (2) TSH  $< 0.34$  mIU/mL or (3) FT4  $< 0.47$  ng/mL or (4) FT4  $> 1.41$  ng/mL. Study medication will be discontinued if any of the criteria are met. Unblinded Study Personnel will maintain a document for each participant with the Month 2 lab results. The document details the criteria for study medication discontinuation and process of notification. The document will be stored in the Unblinded Study Personnel binder in the Research Pharmacy office (a locked, private office) inside the Outpatient Pharmacy area (locked, private area). The SC will collect a copy of the document from Unblinded Study Personnel once the participant completes the study. The copy will be maintained in the participant folder in a locked file cabinet in a private office. The PI will not be alerted to study medication discontinuation. She may inadvertently become aware of study medication discontinuation, but she will not be informed of the reason (hypothyroidism or hyperthyroidism at Month 2) in order to maintain the blind through the planned analysis. Study medication may also be discontinued in the case of early termination (participant decision to withdraw, Investigator decision to withdraw or joint decision). In this case, the PI may be alerted to study medication discontinuation and study medication assignment.

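### The PI may withdraw participants from the study with no provision for further follow-up, putting Month 6 data and the per-arm completion rate at avoidable risk

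*Combined protocol and SAP*

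**What the plan says.** The protocol has two routes out of treatment.

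- **Stopping study medication.** Under Compliance and Withdrawal, when the participant or the PI stops the medication, the participant is asked to "continue the study (including follow-up visits, blood collection and study questionnaires) without continuing the study medication". Those who decline are treated differently: "If the participant does not agree, they will be classified as withdrawn from the study". The Study Medication Discontinuation Criteria section applies the same approach to laboratory-triggered stops: "The participant will be followed per protocol (following discontinuation of study medication) unless they decide to withdraw from the study".
- **Withdrawal from the study.** Compliance and Withdrawal then adds: "The PI may also withdraw participants from the study. This may occur in the event of inter-current illness, adverse events, protocol violations, non-compliance", or for administrative reasons. Safety Considerations repeats this power for illness and adverse events. No compliance level or type of violation is named as the trigger; the 80-100% self-report figure only defines good compliance. No follow-up after such a withdrawal is described, and "Participants withdrawn from the study will not be replaced".

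On analysis, the plan states: "Analyses will be based on the intention-to-treat principle". Planned Analysis includes a completion rate for each arm in the primary feasibility outcome, without defining completion. Complete-case analysis applies if less than 5% of data are missing and the missingness is found to be at random. Otherwise multiple imputation is to be explored.

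**The concern.** Adverse events, intercurrent illness, protocol violations and non-compliance all arise after randomization. In a trial that replaces a long-term drug with placebo, any of them may be linked to the assigned arm or to how the participant feels. If such participants leave the study rather than only the medication, their Month 6 scores are lost, although an intention-to-treat analysis needs them and the participants might have agreed to provide them.

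Two results are exposed. The secondary ThyPRO non-inferiority comparison could be distorted if the people lost differ from those who remain. The completion rate would mix participants' own decisions with the PI's, so it would say less about the retention that the full-scale trial should expect.

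**Working it through.** **1. Does withdrawal by the PI end data collection?** No sentence says so. Three places point that way:

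- Compliance and Withdrawal describes continuing the study as visits, blood collection and questionnaires, and uses withdrawn for people who decline these.
- Study Medication Discontinuation Criteria classes an investigator's decision to withdraw as early termination.
- Data Collected offers an unscheduled early-termination visit, but it is optional and cannot supply a Month 6 measurement.

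The fair reading is that follow-up after a PI withdrawal is not provided for, and that following the text as written would probably lose Month 6 data.

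**2. The plan's loss allowance.** Sample size estimates gives 23 per group, a drop-out rate under 10%, and 50 in total. 2 × 23 = 46, and 46 / (1 − 0.08) = 50, so the step reproduces. The allowance is 50 − 46 = 4 losses from all causes. (The 23 itself does not reproduce with the 14-point margin, SD 20 and one-sided 5%, which needs 26 per group for 80% power. The section does not state the difference it used, and this point does not depend on it.)

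**3. Cost of each withdrawal.** With 1:1 allocation there are about 25 per arm.

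| PI withdrawals without Month 6 data | Share of 50 | Completion if all in one arm |
|---|---|---|
| 1 | 2% | 24/25 = 96% |
| 2 | 4% | 23/25 = 92% |
| 3 | 6% | 22/25 = 88% |
| 4 | 8% | 21/25 = 84% |
| 5 | 10% | 20/25 = 80% |

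Two such losses stay under the 5% missing-data limit; three pass it. Five reach 10%, which is no longer less than 10%.

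**4. Possible shift in an arm mean.** If k of 25 participants are lost and their scores average D points worse than the rest, the retained mean differs from the full mean by (k/25) × D. Both k and D are assumptions.

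- k = 1, D = 10: 0.4 points
- k = 3, D = 14: 1.7 points
- k = 5, D = 20: 4.0 points

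The margin is 14 points. In the placebo arm the shift favours non-inferiority; in the LT4 arm it goes the other way.

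**5. Worst-case type I error.** Simulation: 25 per arm, SD 20, true difference 14 (the null boundary), one-sided 5%, ANCOVA on baseline (gender omitted). The two placebo participants with the worst 6-8 week scores are dropped before a complete-case analysis. The documents give no correlations between visits, so a range was assumed.

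| Assumed correlations | Type I error |
|---|---|
| All equal, 0.3 to 0.7 | about 6-7% |
| 6-8 week with Month 6 at 0.7 to 0.9, above the baseline correlations | about 8-12% |
| Two placebo participants dropped at random | about 5% |

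The inflation comes from selective loss, not from loss as such.

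**The case against.** The strongest reply is that the main arm-related exit is already protected. Laboratory-triggered stops and PI medication stops both keep willing participants in follow-up, the PI is listed as blinded, and the withdrawal clause is only permissive. The trial is also a pilot with feasibility as its primary outcome, and the missing-data rule does not allow complete-case analysis unless missingness is small and found to be at random. All of this stands, and it narrows the gap to discretionary removal from the study.

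It does not close the gap. Blinding limits deliberate selection, but symptoms or adherence that differ by arm would still produce withdrawals that differ by arm. Loss that depends only on recorded 6-8 week scores can count as missing at random in the technical sense, so two such losses (4%) could still lead to complete-case analysis. An imputation model that used those scores could recover much of the loss, but the plan specifies no model.

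A reader might infer three stronger things that the documents do not support:

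- **That the protocol orders data collection to stop.** The wording that ends data collection and contact defines withdrawal by the participant. For withdrawal by the PI the text is silent.
- **That the clause contradicts intention-to-treat.** That principle governs analysis by assigned arm. The clause creates missing data that strain it.
- **That the result is biased towards non-inferiority.** This needs poor scorers to be removed mainly from placebo. The listed reasons are not defined by symptom score, and removing poor scorers from the LT4 arm would bias the other way.

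**Conclusion.** The concern holds as a gap in the withdrawal text that is cheap to close. Withdrawal of a participant by the PI has no follow-up provision, unlike every medication-stop route in the same protocol. Each such withdrawal costs about 4 points of its arm's completion rate and one of four planned losses, assuming 25 per arm and that someone withdrawn before Month 6 is not counted as a completer.

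The effect on the ThyPRO comparison cannot be estimated, because the documents give neither a withdrawal frequency nor visit correlations. The 6-12% type I error is a worst-case illustration that rests on the assumed correlations and on the two losses being the worst 6-8 week scorers on placebo. It is not a forecast. The change should be made, but the gap does not undermine the design.

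**What to change.** Leave decisions about study medication as the protocol has them. In Compliance and Withdrawal, state that a participant whom the PI would withdraw for adverse events, intercurrent illness, protocol violations or non-compliance is offered the follow-up route already given there: visits, laboratory tests and questionnaires to Month 6, if the participant agrees. Align Study Medication Discontinuation Criteria and Safety Considerations with this.

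In Planned Analysis, state that these data are analysed by assigned arm, define completion, and report PI-initiated and participant-initiated losses separately within each arm's completion rate. It is not necessary to limit study withdrawal to withdrawal of consent alone; discretion for administrative reasons can remain, provided those losses are reported.

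The cost is a few sentences, plus some follow-up visits for people who would otherwise have left. Those visits are already scheduled for every participant.
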